7.3. Multi-Center Studies

This is a multi-center study. Given the small sample size of the study, no site effect will be considered in any statistical analysis.

7.4. Multiple Comparisons / Multiplicity

No adjustment for multiple comparisons will be conducted. The *P* values will not be adjusted for multiple comparisons and be reported/interpreted according to the nominal levels of significance.

7.5. Examination of Subgroups

Analysis will be performed for each histological type cohort, with Cohort 2 described as Stage 1 or Stage 2. An adverse event incidence table will be presented with subjects grouped by starting dose – 600 mg BID or 900 mg BID. In addition, efficacy data will be grouped and presented with the following subgroups:

- All HNSCCs
- All HNSCCs with HRAS VAF ≥ 20% and serum albumin ≥ 3.5 g/dL or HRAS VAF ≥ 35%. ("High VAF")
- SCC Other (Cohort 3)
- SCC Other (Cohort 3) with HRAS VAF ≥ 20% and serum albumin ≥ 3.5 g/dL or HRAS VAF ≥ 35%. ("High VAF")
- All SCCs including HN (Cohorts 2/Stage 2 and 3 combined)
- All SCCs including HN (Cohorts 2/Stage 2 and 3 combined) with HRAS VAF ≥ 20% and serum albumin ≥ 3.5 g/dL or HRAS VAF ≥35%. ("High VAF")

7.6. Handling of Dropouts or Missing Data

Where individual data points are missing because of insufficient samples, dropouts, or other reasons, the data will be analyzed based on reduced denominators. For survival analysis, dropouts without confirming events will be treated as censored.

7.7. Outlier Handling

Potential data entry errors manifested as outliers will be handled in the data management process through edit checks.

Protocol KO-TIP-001

7.8. Adustments for Covariates

Not applicable.

8. SUMMARY OF STUDY POPULATION DATA

All data will be summarized by cohort. A subgroup analysis will further summarize data according to HRAS status and albumin levels at baseline (see Section 7.5). A single safety table will be presented by starting dose (600 mg or 900 mg).

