The second 7-day schedule study was conducted in patients with relapsed/refractory AML (Kirschbaum 2011). Tipifarnib was administered bid on days 1–7 and days 15–21 of 28-day cycles at doses up to 1600 mg bid (Kirschbaum 2011). At the 400 mg bid dose level, a grade 5

hepatorenal failure occurred, potentially related to the study drug. There were no additional DLTs reported at 600, 800 or 1000 mg bid dose levels. At the 1200 mg bid dose level, a grade 3 creatinine elevation was seen in one patient out of 6 treated. At the 1400 mg bid dose level, one patient experienced a grade 4 hypotension and a rising grade 2 creatinine that were dose limiting, and a second patient had a rising grade 2 creatinine that resulted in treatment discontinuation and was therefore considered dose limiting. At the 1600 mg dose level, grade 3 liver function tests and a rising grade 2 creatinine were dose limiting, and in a second patient, a rapidly rising creatinine was seen and treatment stopped. As a result, the 1200 mg bid dose was established as the MTD and 7 additional patients treated. Sixteen patients were treated at the 1000 and 1200 mg dosing levels, with 3 of them experiencing complete responses. No formal responses were seen among patients treated at the lower dose levels.

Based on these data, the tipifarnib regimen to be investigated in the current study was modified to a starting dose of 900 mg, po, bid on days 1-7 and 15-21 of 28-day treatment cycles. Preliminary data from KO-TIP-001 indicate a tolerability that is broadly similar to the safety profile observed of other tipifarnib regimens in prior clinical studies which administered tipifarnib daily in a 21-day on, 7 days off treatment cycle schedule. The most common AES of tipifarnib including hematological events, gastrointestinal disturbances (nausea, vomiting and diarrhea) and fatigue have been monitorable and manageable with protocol defined assessments and management of toxicity guidance. Dose reduction to 600 mg has been able to reduce tipifarnib-related toxicity and several subjects have maintained their response and continued on treatment for over 1 year.

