Given these preliminary observations and in discussion with study investigators, the starting dose has been reduced to 600 mg, po, bid on days 1-7 and 15-21 of 28-day treatment cycles as part of amendment 5 to the study protocol. In the absence of unmanageable toxicities, subjects may continue to receive tipifarnib treatment for up to 12 months in the absence of disease progression and unmanageable toxicity. Stepwise 300 mg dose reductions to control treatment-related, treatment-emergent toxicities are also included in this protocol amendment. Treatment may continue beyond 12 months upon agreement of the Investigator and Sponsor.

Ongoing subjects receiving the 21-day schedule will be allowed to switch to the 7-day schedule at the discretion of the investigator. Similarly, ongoing subjects receiving 900 mg bid will be allowed to maintain that dose or switch to 600 mg bid at the discretion of the investigator.

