8.4. Dosing and Extent of Exposure

Number of treatment cycles and average dose intensity per cycle will be summarized for the ASaT and PP populations. Dose intensity is defined as the mean % compliance per treatment cycle, where compliance = (actual dose/planned dose)*100. A summary will also be presented for the frequency and incidence of drug modification (dose reduction, dose interruption, dose increase, or drug withdrawn), which will include summary statistics for the number of dose modifications if any per subject.

Data for study drug dispensing and dosing will be presented in listings.

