10.1. Adverse Events

Adverse events will be coded using the latest available version of the Medical Dictionary for Regulatory Activities (MedDRA) Version 19.0. Treatment-emergent adverse events are defined as adverse events that start on or after the first dose of study drug and within approximately 30 days of the last administration of study drug. Adverse events will be summarized by the number and percentage of subjects who experienced the event, according to system organ class and preferred term. A subject reporting multiple cases of the same adverse event will be counted once within each system organ class and similarly counted once within each preferred term.

Unless specified otherwise, the denominator for these calculations will be the number of subjects who received at least one administration of tipifarnib, irrespective of the total number of doses or treatment cycles administered. These conventions will be appropriately modified to calculate AE incidence rates separately for each cycle that study therapy is administered. AE incidence rates may also be calculated based on other measures of subject exposure (e.g., total number of treatment cycles administered).

AE durations will be calculated using all TEAEs. For AEs that are still ongoing at the end of study, we will use either death or the last contact date as the end of AE stop date for calculation the duration of AEs. Median, minimum and maximum of AE durations will be reported.

AEs will also be summarized by NCI-CTCAE version 4.03 severity grade and by relationship to study drug. Additional summaries may also be provided for SAEs, and events resulting in the permanent discontinuation of therapy. All AEs will be included in individual subject listings.

An overall view of TEAEs will be provided, which will include the total number of TEAEs, number of subjects with TEAEs, study drug-related TEAEs, Serious TEAEs, study drug-related Serious TEAEs, Grade 3 or higher study drug-related TEAEs, deaths within 30-days of administration of study-drug, and AEs leading to permanent discontinuation of study drug. Additionally, a corresponding overall view of exposure-adjusted AE incidence will be provided, which will present exposure-adjusted incidence rates (calculated as the mean number of events per treatment cycle) with corresponding 95% confidence intervals.

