Summary tables will be provided which present the incidence of TEAEs by SOC and PT; and the incidence of TEAEs by SOC/PT by maximum severity (NCI-CTCAE Grades 1 through 5), overall and by cohort. Corresponding summaries for laboratory-related AEs will also be provided.

A summary of the AE durations for all TEAEs by SOC/PT will be provided.

Summary tables will be provided which present the incidence of study-drug related TEAEs and the incidence of study-drug related TEAEs with severity scores of Grade 3 or higher by SOC/PT.

Protocol KO-TIP-001

Summary tables will be provided which present the incidence of SAEs, the incidence of study drug-related SAEs, the incidence of TEAEs leading to permanent discontinuation of drug, and the incidence of TEAEs by starting dose (600 mg BID versus 900 mg BID), all by SOC/PT.

Summary tables will be provided which present Grade 3 or above chemistry and hematology toxicities by treatment cycle, fatigue (preferred term) by treatment cycle, and gastrointestinal events (SOC) by treatment cycle.

Data on adverse events will be presented in listings.

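### The only output by starting dose is a crude TEAE incidence table, so its 600 versus 900 mg contrast mixes dose with time on treatment and later dose

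*SAP*

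**What the plan says.** SAP 8 makes cohort the default split for all summaries and adds one exception: "A single safety table will be presented by starting dose (600 mg or 900 mg". SAP 7.5 describes it: "An adverse event incidence table will be presented with subjects grouped by starting dose – 600 mg BID or 900 mg BID". SAP 10.1 gives the content: "the incidence of TEAEs by starting dose (600 mg BID versus 900 mg BID), all by SOC/PT". No grade limit is attached, although the related-TEAE table described just before it is limited to grade 3 or higher, so all grades is the natural reading.

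The default denominator in SAP 10.1 is subjects "who received at least one administration of tipifarnib, irrespective of the total number of doses or treatment cycles administered". The same section allows exposure-based rates as an option and plans an exposure-adjusted overview, but ties neither to starting dose. For exposure, SAP 8.4 says "A summary will also be presented for the frequency and incidence of drug modification", alongside dose intensity, again with no starting-dose split.

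Protocol 9.4 reports that reducing 900 mg starters to 600 mg lessened toxicity and that "several subjects have maintained their response and continued on treatment for over 1 year". When Amendment 5 lowered the starting dose, "ongoing subjects receiving 900 mg bid will be allowed to maintain that dose or switch to 600 mg bid". Protocol 9.4 also describes a first subject treated under an earlier protocol version on a 21-day schedule at 300 mg bid.

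**The concern.** Safety and tolerability is the secondary objective, and Protocol 9.4 gives tolerability observations at 900 mg as background to the Amendment 5 change. A reader will use the starting-dose table to compare the two starts, since nothing else in the plan separates them. Two features undermine that use.

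- Crude incidence rises with time on treatment, and the two groups may have been treated for different lengths of time.
- Events that a 900 mg starter has after reduction or switch to 600 mg are counted under 900 mg.

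Meanwhile the outputs closest to tolerability (severe related events, discontinuations, dose changes, dose intensity) pool the starting regimens. The SAP synopsis and section 4.1 name only the 600 mg start, so a reader could take the pooled figures as describing it.

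**Working it through.** **Figure to reproduce.** None. The documents give no event rate, exposure or group size by starting dose.

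**Step 1: trace the planned outputs.**

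| Output | SAP section | Split by starting dose? |
|---|---|---|
| TEAE incidence by SOC/PT | 7.5, 8, 10.1 | Yes |
| TEAEs by maximum severity | 10.1 | No (overall and by cohort) |
| Related TEAEs of grade 3 or higher | 10.1 | Not stated |
| SAEs; TEAEs leading to discontinuation | 10.1 | Not stated |
| Grade 3 or higher laboratory toxicity by cycle | 10.1 | Not stated |
| Exposure-adjusted overview | 10.1 | Not stated |
| Dose intensity; dose modifications | 8.4 | Not stated |

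Section 8 speaks of one table only, so these others cannot be read as also split by starting dose.

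**Step 2: how exposure acts on a crude contrast.** All hazards and cycle counts here are assumptions. Take a constant first-event hazard per cycle, h900 and h600. A 900 mg starter has k cycles at 900 mg and then m at 600 mg; a 600 mg starter has c cycles.

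- Crude incidence, 900 mg column: 1 − exp(−(k·h900 + m·h600))
- Crude incidence, 600 mg column: 1 − exp(−c·h600)
- First two cycles (k = 2): 1 − exp(−2·h900) against 1 − exp(−2·h600)

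*Gap created.* h900 = h600 = 0.10, k = 2, m = 11, c = 4 to 6. The 900 mg column is 1 − exp(−1.3) = 72.7%. The 600 mg column is 1 − exp(−0.4) = 33.0% to 1 − exp(−0.6) = 45.1%. The gap is 28 to 40 points with no dose effect. First two cycles: 18.1% against 18.1%.

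*Gap reversed.* h900 = 0.20, h600 = 0.10, k = 2, m = 0, c = 6. The columns are 1 − exp(−0.4) = 33.0% and 1 − exp(−0.6) = 45.1%, so the dose with twice the hazard shows 12 points fewer. First two cycles: 33.0% against 18.1%.

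*Gap hidden.* h900 = 0.30, h600 = 0.10, k = 2, m = 0, c = 6. Both columns are 1 − exp(−0.6) = 45.1% despite a threefold hazard. First two cycles: 45.1% against 18.1%.

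*A rate per cycle by starting dose is not enough.* With h900 = 0.20, h600 = 0.10, k = 2, m = 11, the 900 mg rate is (2 × 0.20 + 11 × 0.10)/13 = 0.115. Against 0.10 the ratio is 1.15, when the true ratio is 2.

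**Step 3: how much 600 mg time could sit under 900 mg.** The protocol version carrying Amendment 5 is dated 01 November 2018 (SAP title page), and the later data cut in SAP 7.2 is 30 September 2020. That is 699 days; 699/28 = 25.0 cycles, or 699/30.4375 = 23.0 months. This is a ceiling at that cut for someone who switched under Amendment 5, not a documented amount.

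**Step 4: what a better table could resolve.** Split the 75 planned subjects 20/55 to 50/25 between 900 and 600 mg starts (assumed), two-sided 0.05, normal approximation with pooled null variance. For 45% against 30% with 20 and 55 subjects, the null standard error is √(0.34 × 0.66 × (1/20 + 1/55)) = 0.1237 and the alternative one is √(0.45 × 0.55/20 + 0.30 × 0.70/55) = 0.1273. Then (0.15 − 1.96 × 0.1237)/0.1273 = −0.726, a power of 23%. Over the range of splits, power is 23% to 26% for 45% against 30%, and 66% to 75% for 60% against 30%.

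**The case against.** The SAP never says that this table should show whether Amendment 5 improved tolerability. No objective or hypothesis compares doses, and grouping by starting dose is an ordinary descriptive convention. This stands: the table should not be judged as a failed test. It still sets 600 against 900 mg BID side by side and will be read as a contrast.

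A reader might infer that over a year of 600 mg exposure is charged to the 900 mg column. The documents do not say so. Protocol 9.4 gives total time on treatment for several subjects, not time at 600 mg.

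A reader might also infer that the tolerability of a 600 mg start cannot be read from the output at all. That goes too far. Protocol Table 2 only steps down from 600 mg and section 9.5 limits re-escalation to the original dose, so the 600 mg column does describe TEAE incidence by SOC/PT from that start.

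Some material already exists: incidence by cycle, optional exposure-based rates, an exposure-adjusted overview, dose-modification summaries and full listings. The companion table shells, which are not among the documents, might add columns. None of these is assigned to starting dose in the SAP, so they make the repair easy without making it.

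The 21-day 300 mg bid group may be very small. Protocol 9.4 describes one such subject and gives no count, so a footnote is enough.

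**Conclusion.** The point holds in a limited form. As written, the 600 versus 900 mg contrast mixes starting dose with time on treatment and later dose, and the other tolerability outputs pool starting regimens. Size and direction are unknown: the gaps in the working (28 to 40 points created, 12 points reversed, a threefold hazard hidden) rest wholly on assumed hazards and exposures and show only what the table permits.

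The primary endpoint and the two-stage decision rules are untouched. The groups are non-randomised and were enrolled in different periods, and power is low under the assumed splits, so a repaired table would describe the two starts without settling whether the dose change helped. This is a cheap improvement.

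**What to change.** Amend SAP 7.5, 8, 8.4 and 10.1 before the database is frozen:

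- Show the starting-dose TEAE table for a fixed common window (Cycles 1-2 from first dose, all treated subjects, regardless of dose reduction) beside the whole-treatment crude incidence.
- Add starting-dose columns to the planned tables of grade 3 or higher related TEAEs, SAEs, TEAEs leading to discontinuation, dose modifications and dose intensity.
- Give events per cycle by dose at onset as a supportive summary.
- Footnote where subjects who started on the 21-day 300 mg bid schedule are counted.
- Label all of this non-randomised and descriptive.

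Counting events only while a subject is on the assigned starting dose should not be the main comparison. Under Protocol 9.5 toxicity triggers the reductions, so that rule would censor informatively and drop later events in the subjects who tolerated the dose worst.

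The cost is SAP wording and a few columns on planned tables, using data already collected. The downside is small groups from different enrolment periods. The fixed window equalises the counting period but not cohort mix, calendar time or dropout within the first two cycles.

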8.1. Subject Disposition

Subject disposition will be provided for all subjects screened. A summary table will present the total number of subjects screened, total number enrolled, and total number in each analysis population. Among subjects who received any study drug, this summary will also present the frequency and percentage of subjects who discontinued treatment and came off study. The primary reasons for discontinuation of treatment, and for end of study will be tabulated.

Detailed subject disposition information, as well as eligibility and analysis population assignment will be provided in listings.

8.2. Protocol Deviations

A detailed listing of all protocol deviations will be included.

8.3. Demographics and Baseline Characteristics

Descriptive statistics of demographic measurements at screening such as age, sex, ethnicity, race, measurements of height and weight, and ECOG performance status score at screening will be summarized for the ASaT and FAS populations.

Medical and surgical history / physical findings will be coded using Medical Dictionary for Regulatory Activities (MedDRA) version 19.0 and summarized by system organ class (SOC)/ preferred term (PT) for enrolled subjects.

Summaries of cancer history at screening by cancer diagnosis and stage will be provided for enrolled subjects. Thyroid cancer subtype at screening will be summarized for enrolled subjects. Prior anti-cancer therapy, cancer surgery and radiation therapy will be summarized for both the ASaT and FAS populations. For prior anti-cancer therapy, descriptive statistics on the number of regimens per subject, best overall response on last prior therapy, and last therapy progression free survival will be presented. Progression free survival on last prior therapy will be calculated as follows:

((Progression Date – Earliest Treatment Initiation Date of Most Recent Prior Cancer Therapy) + 1)/30.4375. If date of progression is not available for the last prior therapy, then the start date of Tipifarnib will be used to calculate PFS.

Kaplan Meier curves will present PFS on last prior therapy for the FAS population by cohort and PFS of last prior cancer therapy for the subgroups.

Protocol KO-TIP-001

Descriptive statistics will be presented for the number of cancer surgery procedures per subject, the number of prior radiation therapies per subject, and the radiation intent (adjuvant, salvage, palliative, unknown).

Data on individual subject demographics; baseline medical, surgical history/physical findings; HRAS status at screening; cancer history at screening; and prior anti-cancer therapy, prior cancer surgery, and prior radiation therapy will be displayed in listings.

8.4. Dosing and Extent of Exposure

Number of treatment cycles and average dose intensity per cycle will be summarized for the ASaT and PP populations. Dose intensity is defined as the mean % compliance per treatment cycle, where compliance = (actual dose/planned dose)*100. A summary will also be presented for the frequency and incidence of drug modification (dose reduction, dose interruption, dose increase, or drug withdrawn), which will include summary statistics for the number of dose modifications if any per subject.

Data for study drug dispensing and dosing will be presented in listings.

8.5. Prior and Concomitant Medications

Prior cancer therapies, and prior and concomitant medications (other than cancer treatment) will be coded by WHO Drug Dictionary (WHODD version Dec 2014 B2) and summarized by preferred ATC Level 4 text and preferred drug name. For drugs not having ATC Level 4, ATC Level 3 text will be used.

Data for prior cancer therapies prior and concomitant medication (other than cancer treatment), and for non-drug treatments or procedures will be presented in listings.

9. EFFICACY ANALYSES

Summaries for efficacy data will be presented by cohort and by subgroup.

9.1. Primary Efficacy Analyses

The objective response rate (ORR) of tipifarnib in subjects with locally advanced unresectable or metastatic, relapsed and/or refractory, HRAS mutant non hematological malignancies will be estimated. The primary endpoint will be response assessments according to RECIST 1.1

The estimate of the objective response rate will be calculated based on the maximum likelihood estimator (i.e., crude proportion of subjects whose best overall response is Complete Response (CR) or Partial Response (PR)). The estimate of the objective response rate will be accompanied by 2-sided 95% Confidence Interval (CI). When $N\hat{p} > 5$, where N is number of subjects, the 95% CI can be estimated using the Wilson, score test based, method.

Protocol KO-TIP-001

A summary of the ORR will be presented for the FAS population. A corresponding summary for the PP population will be presented as a sensitivity analysis. In addition, the data will be presented for the subgroups as described in Section 7.5.

Data on tumor assessment information, target tumor assessment, non-target tumor assessment, new lesion assessment and overall response assessment will be displayed in listings.

9.2. Exploratory Efficacy Analyses

The duration of objective response (DOR) will be calculated for subjects who achieve CR or PR. For such subjects, the DOR is defined as the number of days from the start date of PR or CR (whichever response is achieved first) to the first date that progressive disease is objectively documented. Disease progression will be determined by the Investigator using RECIST (version 1.1). The DOR will be right-censored at the date for subjects who achieve CR or PR and meet 1 of the following conditions: 1) when non-protocol anticancer treatment started before documentation of disease progression, 2) when death prior to documented disease progression or documented disease progression after more than 1 missed disease assessment visit, or 3) when alive and does not have documentation of disease progression before a data analysis cutoff date. (Therefore, analysis cutoff date will be used as the censoring date).

Progression free survival (PFS) will be defined as the time (in months) from first dose (Cycle 1 Day 1) to either first observation of progressive disease or occurrence of death due to any cause within 126 days (approximately 2 time intervals for tumor assessments) of either first administration of tipifarnib or the last tumor assessment. Observation of progressive disease can be by either documented radiographic progression (i.e., scan results) or documentation of symptomatic or clinical progression agreed upon and documented by investigators. In subjects without a progression date or with a death date more than 126 days after the first administration of study drugs or the last tumor assessment, the PFS time should be censored on the date of last tumor assessment or date of first administration of study tipifarnib. PFS analyses should consider tumor assessments after treatment discontinuation or metastatic surgery.

The DOR and PFS, will be summarized descriptively using the Kaplan-Meier (KM) method. The 25th, 50th, and 75th percentiles of the Kaplan-Meier distribution will be used to describe the median response duration and median PFS.

The median DOR and PFS and corresponding pointwise 95% confidence interval will be displayed by cohort for the FAS population and for the PP population, and for the subgroups.

The KM curves of DOR and PFS by each cohort will be displayed for the FAS population, the PP Population, and for the subgroups in figures. A per subject summary of DOR, such as treatment initiation date, progression date, first response date, durations, censoring status, best overall response, and analysis population inclusion, will be provided. Similarly, a per subject summary of PFS, including enrollment date, treatment initiation date, progression date, duration, censoring status, best overall response, and analysis population inclusion, will also be provided.

Subgroup analysis may be conducted to estimate PFS and DOR in the subset of subjects with partial response. Sensitivity analysis may be conducted to assess the impact of the median survival estimation method. Interpolation based estimates can be used to estimate the median

Protocol KO-TIP-001

survival whenever the sample size is small or there is not sufficient information (events) to robustly estimate the median survival based on KM function.

Further analysis may include the comparison of the PFS between tipifarnib and prior therapies. A *P* value comparing the two PFS profiles (prior therapy and the current using tipifarnib) will be obtained using Wei-Lin (Cox regression based) robust estimator.

If biomarkers including somatic mutations in archival tumor tissue have been successfully obtained for enough subjects, the relationship of the detection of tissue biomarkers potentially related to tipifarnib activity will be investigated as described in the protocol.

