3.3. Exploratory Objective and Endpoints

Exploratory Objective 1: To determine the antitumor activity in terms of progression free survival (PFS), and duration of response (DOR) of tipifarnib in subjects with locally advanced

Protocol KO-TIP-001

unresectable or metastatic, relapsed and/or refractory, HRAS mutant non hematological malignancies.

Exploratory Endpoints 1: PFS, and DOR according to RECIST 1.1.

Exploratory Objective 2: To explore the feasibility of collecting archival biopsies and analyzing these biopsies for the detection of tissue biomarkers potentially related to tipifarnib activity.

Exploratory Endpoints 2: Molecular analyses of archival tissue samples.

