Tumor assessments will be performed at screening and approximately every 8 weeks starting at the end of cycle 2 for the first 6 months (Cycles 2, 4, 6) and then every 12 weeks (Cycles 9, 12, 15, etc.), or sooner if deemed necessary by the Investigator, and will continue until disease progression. A tumor assessment will be performed upon treatment discontinuation (End of Treatment visit) if the reason for discontinuation is other than disease progression and no tumor assessment was performed in the prior 8 weeks, or a tumor assessment is required for the confirmation of response to treatment. Subjects who discontinue treatment for reasons other than disease progression must continue tumor assessments until disease progression, withdrawal of subject's consent or initiation of another anticancer therapy. Determination of objective tumor response will be performed by the Investigator. However, tumor images may be de-identified of subject's personal information at the clinical sites and collected by the Sponsor or designee to undergo an external independent radiological review if the sponsor deems it necessary for the final assessment of the efficacy of the treatment. If an independent radiological review were to be conducted, reviewers would be blinded to Investigator's tumor response assessments. An independent review committee charter would be generated to provide the specific procedures that would be filed with Institutional Review Board (IRB) and regulatory authorities.

Subjects with a solitary site of disease who have experienced a response may be considered for surgical resection. Subjects with a Partial Response (PR) and residual disease after salvage surgery are eligible to continue on study therapy.

Upon disease progression, all subjects in the study cohort will be followed approximately every 12 weeks for survival and the use of subsequent therapy until either death or 12 months after accrual in the subject's study cohort has been completed, whichever occurs first. Information on survival and subsequent anticancer therapy may be collected by phone.

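### SAP 9.2 censors a responder's death before progression in duration of response, while PFS in the same section counts a death within 126 days of the last tumor assessment as an event

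*SAP*

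**What the plan says.** In SAP 9.2, DOR runs from the first CR or PR to the first objective documentation of progressive disease. Death is not named as an event. The censoring rule begins "The DOR will be right-censored at the date for subjects who achieve CR or PR" and lists three conditions:

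1. Non-protocol anticancer treatment started before progression.
2. "when death prior to documented disease progression or documented disease progression after more than 1 missed disease assessment visit".
3. The subject is alive without progression at the data cutoff. A parenthesis follows directly: "Therefore, analysis cutoff date will be used as the censoring date".

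The PFS paragraph of the same section treats death differently. It counts "occurrence of death due to any cause within 126 days" of first dosing or of the last tumor assessment. For later deaths it names a date: "the PFS time should be censored on the date of last tumor assessment", or the date of first dosing.

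Protocol 12.2.1 also ends DOR at progression only. Its second censoring condition joins death and documented progression in front of one missed-visit phrase, so that phrase can be read as applying to both. The SAP has separated them and given death its own qualifier. SAP section 14 lists two changes from the protocol, the addition of overall survival and a subset sensitivity analysis for PFS and DOR. It does not list this one.

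**The concern.** Response ends at death. Censoring the death tells the Kaplan-Meier estimator that the subject could still have been in response later, at the same progression risk as those who remain under observation. That is informative censoring in the direction favourable to the drug. In a single-arm study DOR is read next to the response rate, and SAP 9.2 reports it by cohort, by population and by subgroup.

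Two drafting faults add to this. The section says that DOR is censored at a date without saying which one. And the same responder, dying soon after a scan, is an event in one curve and censored in the other, with no reason given and no statement that DOR is meant to be a pure time-to-progression measure.

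**Working it through.** The documents give no DOR median, no DOR sample size and no count of responder deaths, so there is no plan figure to reproduce. The check covers the direction, then the size under stated assumptions.

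**1. Status of a responder who dies without documented progression, within 126 days of the last tumor assessment**

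| Endpoint | SAP 9.2 rule | Status |
|---|---|---|
| PFS | death from any cause inside the window | event at death |
| DOR | condition 2, death before progression | censored |

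**2. Direction.** With the death counted, the Kaplan-Meier curve is multiplied at that time by 1 − d/n, where d is the number failing and n the number at risk. With the death censored at the same date, its contribution to d is removed, while every risk set is unchanged. So the curve with deaths censored is never below the curve with deaths counted, and its median is never shorter.

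**3. Size under constant hazards.** Let λ be the total failure hazard in responders and f the share of first failures that are deaths without documented progression (assumed). Censoring the deaths leaves an event hazard of (1 − f)λ, so

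median = ln 2 / [(1 − f)λ] = true median / (1 − f).

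- f = 10%: 1/0.9 = 1.11, or +11%
- f = 20%: 1/0.8 = 1.25, or +25%
- f = 30%: 1/0.7 = 1.43, or +43%
- f = 0: no change

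For an assumed true median of 6.0 months these give 6.7, 7.5 and 8.6 months.

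**4. Size in a small sample.** Take 30 HNSCC subjects and the 30% design alternative (SAP section 5): 30 × 0.30 = 9 responders. Assume exponential durations with median 6.0 months and a cutoff 24 months after response. In 4,000 simulated samples per setting, the typical Kaplan-Meier median was 6.0 months with death counted. With death censored at its date it was 6.8, 7.6 and 8.6 months for f = 10, 20 and 30%.

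**5. How often one trial's reported median moves.** Comparing the two rules within the same simulated sample of nine:

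- At f = 10% the median is identical in about 60% of samples (midpoint rule) or 66% (first time the curve is at or below 0.5). About 42% of samples contain no responder death at all.
- At f = 20% it is identical in 34 to 41%.

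With nine complete durations, censoring one of them leaves the median unchanged in 4 of 9 positions (midpoint rule) or 5 of 9 (first time at or below 0.5).

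**6. Worked example (invented data).** Durations are 2, 3, 4, 5, 6, 8, 10, 12 and 14 months, with deaths at 3 and 6.

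- Deaths counted: the curve at 6 months is 4/9 = 0.44, so the median is 6.
- Deaths censored at death: 8/9 × 6/7 × 5/6 = 0.63 after month 5, then × 3/4 = 0.48 at month 8, so the median is 8.

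**The case against.** **The rule may be deliberate.** The protocol also ends DOR at progression only, so the SAP follows it on the event. That stands. It is why the progression-only version should be kept and shown. It does not remove the bias, and the SAP does not label the rule as a time-to-progression choice.

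**The ambiguity is easily overstated.** Two stronger readings are tempting.

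- A reader might infer that a responder who dies with no missed visits has no status at all. Protocol 12.2.1 permits that reading. The SAP does not naturally permit it, because death there carries its own qualifier and the missed-visit phrase belongs to the repeated reference to progression.
- A reader might infer that deaths are censored at the analysis cutoff, which would carry response past death. In the same simulation that gives 7.1, 8.6 and 11.0 months. But the cutoff sentence follows condition 3, which covers living subjects only, and the phrase about censoring at the date when a condition is met most naturally means the date of death. These larger figures should not be used as the size of the problem.

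**The effect may be small.** At f = 10% the shift lies well inside the sampling spread: in a similar simulation with cutoffs between 12 and 36 months, the interquartile range of the median was about 4.3 to 8.1 months with death counted and 4.8 to 9.3 with death censored. All inputs are assumed, and the simulation has neither missed scans nor censoring for new therapy.

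**Partial mitigations exist.** SAP 9.2 and 9.3 plan per-subject DOR, PFS and survival output, so each case can be seen. SAP 9.2 also allows PFS to be estimated in partial responders, which counts deaths inside the window. That analysis is optional, covers partial responders only and is timed from first dose. None of these corrects the reported median DOR.

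**Conclusion.** The point holds in this form: the SAP states a rule that censors deaths before progression in DOR, the rule conflicts with PFS in the same section, and at the date of death its error can only be zero or toward a longer median. The constant-hazard size is +11, +25 or +43% for an assumed death share of 10, 20 or 30%. It is zero with no such deaths and often invisible in one sample of about nine responders at the low end. The censoring date is badly drafted rather than contradictory. The reworded second condition is an unlisted change from the protocol.

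The documents do not support the inference that any reported median is materially wrong, because they give no responder deaths. Nor do they support any effect on the primary conclusion: DOR is exploratory and descriptive, and the two-stage decision rests on counts of confirmed responses.

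**What to change.** In SAP 9.2:

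- Report DOR as the time from first CR or PR to the earlier of documented progression or death from any cause. Count a death within 126 days of the last tumor assessment, and censor a later death at that assessment, as for PFS.
- Report the protocol's progression-only DOR beside it, with both versions labelled.
- Limit the missed-visit clause to documented progression. It should not govern death: scans are "every 8 weeks starting at the end of cycle 2 for the first 6 months (Cycles 2, 4, 6) and then every 12 weeks" (SAP 4.1), so the second missed scan falls at about 2 × 56 = 112 or 2 × 84 = 168 days, and neither matches 126.
- Name the censoring date for each condition, and limit the cutoff sentence to condition 3.
- Record the change and its date in section 14, including the departure from the protocol's second condition.

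The cost is one SAP paragraph, one derivation, and re-run DOR tables and curves. Death is already needed for PFS and overall survival, so no new data are required. The downside is that the median DOR may be shorter. The change also comes after the April and September 2020 data cuts named in SAP 7.2, in an open-label study. That is why both versions should be shown and the change filed before the database is frozen, as SAP section 2 requires.
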